### 5.1.1 Routine Care Procedures

Patients will undergo cTACE according to the standard of care hospital protocol. Depending on the assigned treatment arm, a lobar or superselective cTACE procedure will be performed.

To perform the superselective TACE technique, the tumor-feeding arteries will be catheterized with a coaxial microcatheter passed through a 5-Fr catheter previously placed either the right or left hepatic artery. The tip of the microcatheter will be placed into the hepatic arterial branch afferent to the segment in which the tumor is located, or if possible the tip of the catheter will be further advanced into the subsegmental branches feeding the tumor. After the microcatheter placement, the chemotherapy mixture will be injected under fluoroscopy, followed by injection of 1% lidocaine and 100-300 micron embospheres.

Nonselective lobar TACE will consist of injection of the same chemotherapy materials used in the superselective procedures into the right or left lobar branches.

The amount of chemoembolization material administered is titrated to the area being treated, i.e., a smaller area (lesion) may be adequately treated with a portion of the prepared chemoembolization material. The chemoembolization material consists of 10cc of chemotherapy, with 50 mg doxorubicin and 10 mg of mitomycin-C mixed 1:1 with Lipiodol (approximately 10cc) giving a total of approximately 20cc. After the chemotherapy is administered, approximately 10cc of 1% lidocaine and 1-2 vials of embospheres measuring 100-300 microns are injected. The amount of 1% lidocaine and embospheres is titrated to each clinical situation.

Intra-arterial chemotherapy materials:

- 10 cc of chemotherapy, with 50 mg doxorubicin and 10 mg of mitomycin-C mixed 1:1 with Lipiodol (approximately 10cc) giving a total of approximately 20 cc.
- 10 cc of 1% lidocaine
- 1-2 vials of embospheres measuring 100-300 microns to achieve angiographic end-point of 2-5 heart beats to clear the contrast column.

Following the chemoembolization procedure, the patient is admitted for observation, pain control, and hydration, and is discharged home once they are stable. The day after the TACE procedure, a non-contrast CT scan is performed to document the deposition of the Lipiodol.

Follow-up imaging, labs, and clinical assessment are done 3-4 weeks following the cTACE procedure.

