### 1.6 Transarterial Chemoembolization Safety Profile

Generally, TACE is a well-tolerated procedure, although side effects are common. Embolization of the liver has been performed for decades for a variety of indications and is well-tolerated. Embolization of solid organs causes a self-limited post-embolization syndrome in the majority of patients, consisting of varying degrees of pain, nausea, vomiting, and fever. This is independent of chemotherapeutic drug use, reason for embolization (e.g. bleeding, tumor), and the organ treated (e.g. liver, kidney, spleen, uterus). With current medical care (e.g. hydration, anti-emetic therapy, and pain control), post-embolization syndrome is well-tolerated and 50% of patients can be discharged from the hospital the day after chemoembolization. The average length of stay is 1.5 days. Liver function is transiently affected with an increase in liver aminotransferase levels. These values usually peak 3-5 days after therapy and return to baseline levels by 10-14 days after embolization. There is no sustained degradation of liver function in properly selected patients who do not meet the well-established exclusion criteria for hepatic artery occlusion, even in the presence of cirrhosis (32). Because most of the injected drug is retained in the liver, systemic toxicity is minimized, with little bone marrow

suppression. The cumulative toxicity is far more limited than is experienced with systemic chemotherapy, which requires protracted drug exposure for an indefinite period of time. Treatment related complications occur in approximately 10% of performed procedures, with mortality rate around 2% (33).

Serious adverse events occur after approximately 5% of chemoembolization procedures. The most common serious adverse events are liver abscess or liver infarction, which occur in approximately 2% of cases each. The 30-day mortality rate is 1% (34-36) (37).

Constitutional symptoms: The post embolization syndrome consisting of transient abdominal pain, ileus, fever and malaise affects 60% to 80% of patients receiving TACE. Prophylactic antibiotics are not routinely administered as the fever is a predictor of treatment response. This fever is a result of tumor necrosis initiated by the therapy.

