Gastrointestinal side effects and complications: Transaminases commonly rise 10 fold. Patients may develop ischemic cholecystitis, hepatic abscess, or biliary strictures. Additionally, a minority of patients will develop nausea/vomiting and ascites.

Endocrine complications: Some patients may develop symptomatic hypothyroidism as a result of retained iodine load.

Hematologic complications: Some patients may develop a leukemoid reaction. Bone marrow toxicity is uncommon occurring in less than 4% of patients and includes neutropenia and thrombocytopenia. A small cohort of patients has developed gastrointestinal hemorrhage as a result of TACE therapy.

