## 5.2 Visit Schedule and Study Evaluation

### Screening

Total 30 patients (up to 40 consented), approximately 15 with HCC and 15 with secondary liver cancer (range: 8-20): Obtain informed consent, screen potential subjects by inclusion and exclusion criteria, register eligible participants, obtain MRI imaging and labwork if not already completed.

Assignment into lobar or  
superselective arm based on  
imaging and history

Lobar arm:  
15 subjects (8-20)

Superselective arm:  
15 subjects (8-20)

### Day 0

PK baseline blood draw performed prior to cTACE.

cTACE procedure, lobar vs superselective approach as assigned.

PK blood draws at: 5, 10, 20, 40 min, 1, 2, 4 hours after cTACE.

### Day 1

PK blood draw 24 hours after cTACE.  
Standard of care non-contrast abdomen CT to ensure Lipiodol administration.

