### Day 21-28

Standard of care clinical followup, H&P, labwork, MRI or CT imaging.  
PK blood draw at 3-4 weeks.

Please see appendices for additional study calendar.

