## 6. Adverse Event Collection and Reporting Requirements

### 6.1 Definitions

An Adverse Event (AE) is defined as any new untoward medical occurrence or worsening of a pre-existing medical condition in a patient and that does not necessarily have a causal relationship with this treatment. An AE can therefore be any unfavorable and unintended sign (including abnormal laboratory finding, for example), symptom, or disease temporally associated with the treatment.

A Serious AE (SAE) is an untoward medical occurrence that at any dose produces any of the following outcomes:

- Results in death;
- Is life threatening (defined as an event in which the subject was at risk of death at the time of the event; it does not refer to an event which hypothetically might have caused death if it were more severe):

- Requires inpatient hospitalization or causes prolongation of existing hospitalization (see NOTE below for exceptions);
- Results in persistent or significant disability/incapacity;
- Is a congenital anomaly/birth defect;
- Is an important medical event (defined as a medical event(s) that may not be immediately life-threatening or result in death or hospitalization but, based upon appropriate medical and scientific judgment, may jeopardize the subject or may require intervention [e.g., medical, surgical] to prevent one of the other serious outcomes listed in the definition above). Examples of such events include, but are not limited to: intensive treatment in an emergency room or at home for allergic bronchospasm; blood dyscrasias or convulsions that do not result in hospitalization.

NOTE:

The following hospitalizations are not considered SAEs:

- Admissions as per protocol for a planned medical/surgical procedure;
- Routine health assessment requiring admission for baseline/trending of health status (e.g., routine colonoscopy);
- Medical/surgical admission for purpose other than remedying ill health state and was planned prior to entry into the study. Appropriate documentation is required in these cases;
- Admission encountered for another life circumstance that carries no bearing on health status and requires no medical/surgical intervention (e.g., lack of housing, economic inadequacy, care-giver respite, family circumstances, administrative).

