## 7. Statistical Methods

### 7.1 Primary Outcome Variable

Pharmacokinetic profile of doxorubicin and doxorubicinol after cTACE for each patient:

- Parameters of PK analysis including peak of the plasma concentration ( $C_{max}$ ), time of maximum concentration, and area under the concentration time-curve (AUC).
- PK profiles for each patient will be correlated with toxicity and tumor burden (size of target lesion), BSA and gender.
- Comparison of PK profile between lobar administration and superselective administration.

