**Study Visit Calendar**

	Day -30 to 0	Day 0 (baseline)	Day 1	Day 21-28
Informed consent	X			
I/E criteria	X			
Medical history, H&P	X			X
Serum/urine pregnancy test (if applicable)	X			
Blood chemistry, hematology/coagulation	X			X
Tumor marker: AFP, CEA, CA 19-9, etc.	X			X
MRI scan, contrast enhanced of the liver	X			X
cTACE procedure		X		
Doxorubicin PK*		X	X	X
Non-contrast CT abdomen (standard of care)			X	
*PK blood samples will be drawn at: baseline (pre-cTACE), 5, 10, 20, 40 min, 1, 2, 4, 24 hours, and at 3-4 week time points after cTACE.

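### Safety labs are scheduled only at screening and Day 21-28, so the peak grade, frequency and onset of transient laboratory toxicity, chiefly transaminase elevation, are not systematically captured

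*Combined protocol and SAP*

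**What the plan says.** **Schedule.** Section 5.1.1 states: "Follow-up imaging, labs, and clinical assessment are done 3-4 weeks following the cTACE procedure". Section 5.2 lists for Day 21-28: "Standard of care clinical followup, H&P, labwork, MRI or CT imaging". In the Study Visit Calendar (section 11) the row "Blood chemistry, hematology/coagulation" is marked at Day -30 to 0 and at Day 21-28, and nowhere else. Day 1 in section 5.2 has "PK blood draw 24 hours after cTACE" and a non-contrast CT, with no safety labs. Section 5.1.2 assays the PK samples for doxorubicin and doxorubicinol only.

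**Expected course.** Section 1.6 says of liver aminotransferases: "These values usually peak 3-5 days after therapy and return to baseline levels by 10-14 days after embolization". The same section adds: "Transaminases commonly rise 10 fold". It gives an average hospital stay of 1.5 days.

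**Use of toxicity data.** The adverse event definition in section 6.1 covers laboratory findings: "An AE can therefore be any unfavorable and unintended sign (including abnormal laboratory finding, for example". The safety outcome (sections 2.2 and 7.2) describes toxicities by kind, grade, how often they occur and how long after the procedure. Toxicity also appears within the primary outcome (sections 2.1 and 7.1): "PK profiles for each patient will be correlated with toxicity and tumor burden (size of target lesion), BSA and gender". Section 7.3 assigns the Kruskal-Wallis test to this and words it in terms of clinical toxicities. Section 6.3 collects adverse events through 3-4 weeks.

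**The concern.** The plan counts abnormal laboratory findings as adverse events and promises their grade, frequency and timing. It schedules no safety lab in the period when, by its own account, the commonly seen laboratory effect rises, peaks and resolves. A symptomatic event can be recorded whenever it happens. A silent laboratory change is recorded only if blood is drawn and tested.

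Two outputs are exposed. The safety tables could show few or no transaminase elevations, and a reader could take that as evidence of little hepatic effect. Any laboratory component of the PK-toxicity correlation would rest on values taken after the usual course has ended, so an absence of association could not be told apart from an absence of measurement. This matters here because section 1.5 motivates the superselective approach partly by less injury to healthy liver and fewer adverse events.

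**Working it through.** The plan states no statistical figure on this point, so there is nothing to reproduce. The check is day arithmetic, with the day of cTACE as day 0.

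**Inputs**
- Scheduled post-treatment labs: day 21 to 28 (sections 5.1.1 and 5.2, Study Visit Calendar).
- Stated aminotransferase peak: day 3 to 5 (section 1.6).
- Stated return to baseline: by day 10 to 14 (section 1.6).
- Average hospital stay: 1.5 days (section 1.6).
- Last PK draw before the follow-up visit: 24 hours, that is day 1 (sections 5.1.2 and 5.2).

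**1. Peak to scheduled lab.** Shortest gap: earliest lab minus latest peak = 21 − 5 = 16 days. Longest gap: latest lab minus earliest peak = 28 − 3 = 25 days.

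**2. Return to baseline to scheduled lab.** Shortest: 21 − 14 = 7 days. Longest: 28 − 10 = 18 days. Even the least favorable pairing leaves a week between the stated resolution and the first scheduled lab.

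**3. Would unscheduled inpatient labs reach the peak?** 3 − 1.5 = 1.5 days and 5 − 1.5 = 3.5 days. At the average stay, discharge comes 1.5 to 3.5 days before the stated peak, so inpatient labs, if drawn, would usually miss it as well.

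**4. How close does the existing 24-hour draw come?** 3 − 1 = 2 days and 5 − 1 = 4 days. It precedes the stated peak by 2 to 4 days. It is still the only fixed draw between the day of the procedure and the follow-up visit.

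**5. Is there a scheduled lab elsewhere?** Sections 5.1.1, 5.2 and 5.4 and the calendar agree with one another. None places chemistry or hematology between the procedure and day 21.

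| Aspect of laboratory toxicity | Seen at Day 21-28? |
|---|---|
| Abnormality persisting at 3-4 weeks | Yes |
| Peak grade of a transient rise | No |
| Frequency of a transient rise | No, if it resolves as section 1.6 describes |
| Time of onset | No; first scheduled detection is Day 21-28 |

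**The case against.** The strongest reply is that this is a PK study. Its synopsis says that it is not driven by a hypothesis, the procedure is standard of care, and safety is secondary and descriptive. Cmax, time of maximum concentration, AUC and the comparison of the two techniques do not depend on safety labs. That stands, and it limits how much weight the point carries.

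Other parts of the reply also stand:

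- **Hepatic toxicity is not invisible to the study.** A reader might infer that it is, but the course in section 1.6 concerns aminotransferases only and is qualified as usual rather than universal. Section 1.6 also lists abscess, infarction, cholecystitis, biliary stricture and ascites, and gives no such resolution time for them. Section 6.3 collects adverse events throughout, so clinically diagnosed events can be recorded.
- **The PK-toxicity test may not have been meant to include laboratory values.** Section 7.3 speaks of clinical toxicities, whereas sections 2.1 and 7.1 say toxicity without qualification and section 6.1 includes laboratory findings. The text is ambiguous. No section names transaminases as the correlation variable, so a spurious null in a planned laboratory analysis cannot be asserted.
- **Inpatient labs may exist.** Patients are admitted under a hospital protocol that is not part of the documents. The plan neither requires such labs nor says that they would be recorded. It is tempting to add that only the sicker patients would be tested, but that depends on a practice the documents do not show.

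What the reply does not remove is the mismatch itself. Continuous adverse event collection does not find a silent laboratory change that nobody tests for, and the safety outcome makes no exception for laboratory events.

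**Conclusion.** The schedule does not systematically capture the peak grade, frequency or onset of transient laboratory toxicity, chiefly transaminase elevation. The size of the mismatch is 16-25 days after the stated peak and 7-18 days after the stated return to baseline. It affects the descriptive safety outcome and any laboratory component of the PK-toxicity correlation. It leaves clinically diagnosed hepatic events, abnormalities persisting at Day 21-28, the PK estimates and the PK comparison between arms intact.

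The conclusion rests on section 1.6 being right about the usual course and on the calendar being followed as written, with no other labs systematically recorded.

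A reader might go further and expect about 0 of 30 patients to show an elevation at the scheduled visit. That only restates the assumption that all 30 follow the usual course. The documents give no distribution around it and no percentage for how common the rise is, so no expected count can be derived.

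**What to change.** 1. **Calendar.** Add chemistry (AST, ALT, bilirubin) and a complete blood count to the existing 24-hour PK venipuncture on Day 1, for every patient. Report change from screening at 24 hours as a uniform early laboratory measure. Nothing in the documents supports making it the sole laboratory toxicity variable.
2. **Scope of conclusions.** State in sections 7.2 and 7.3 that laboratory safety, and any correlation of PK with laboratory values, refer to 24 hours and to persistence at 3-4 weeks, and that the stated day 3-5 peak is not measured.
3. **Unscheduled labs.** Report them separately, and keep them out of the PK-laboratory correlation and any comparison between arms.
4. **Wording.** Say whether the toxicity analysis in section 7.3 includes laboratory toxicity, so that it agrees with sections 2.1, 6.1 and 7.1.

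**Cost.** Additional blood at a draw that already takes place, a routine lab charge for about 30 patients, and a calendar amendment. The gain is partial: 24 hours falls 2-4 days before the stated peak, and the documents give no 24-hour transaminase value to show how much of the rise it would catch. A draw on days 3-5 would address the peak directly, but with an average stay of 1.5 days it would usually mean an extra visit, so it is not asked for here. If labs cannot be added at all, items 2 to 4 still apply, with item 2 limited to persistence at 3-4 weeks.

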### 5.1.2 Research Procedures

Based on previous methodology utilized in our research trial J1306 at Johns Hopkins and other TACE trials, venous blood will be sampled for doxorubicin concentrations just before the cTACE (pre-) and then repeatedly after cTACE at the following time points: 5 minutes, 10 minutes, 20 minutes, 40 minutes, 1 hour, 2 hours, 4 hours, 24 hours, and 3-4 weeks post cTACE. Data will be collected and recorded on the Doxorubicin PK Worksheet.

#### Instructions for processing PK samples:

Blood samples will be collected in a heparinized tube (6 mL) from subjects at the time points on the study collection calendars (baseline, 5, 10, 20, 40 min, 1, 2, 4, 24 hours, 3-4 weeks). Blood samples will be centrifuged at 1000x g (or 3000 rpm) for 10 minutes at 4°C and stored frozen at -20°C or below until analyzed. The samples will be analyzed for total plasma doxorubicin and doxorubicinol at the Analytical Pharmacology Laboratory at the Sidney Kimmel Comprehensive Cancer Center at Johns Hopkins.

#### Shipment of PK samples:

Samples will be kept at the study site and periodically during the study shipped to the APC Laboratory. Unless otherwise stated, samples will be shipped to the Johns Hopkins SKCCC Analytical Pharmacology Core (APC) Laboratory under the direction of [name]., Ph.D. Specimens should be stored through the duration of the PK study and shipped as a batch. A participant's samples should be shipped to the APC lab within 3 months of the last sample's collection date. (i.e., if C1D1 sample is collected on 1/1/2016, all of the participant's samples should be at the APC lab by 4/1/2016). If another set of participant samples can be batched by waiting up to 2 weeks (i.e., 3.5 months), this deviation is allowed.

Samples will be shipped with a copy of the Doxorubicin PK Worksheet to the APC laboratory. Overnight shipments should occur on **Monday** through **Wednesday** (**Tuesday** is the preferred day) except when the following day is a holiday. A fax or call should be placed to the Analytical Pharmacology Core Laboratory prior to shipment providing the shipment tracking information. Samples should be shipped on dry ice to:

Analytical Pharmacology Core Laboratory  
Attn: [name] cTACE doxorubicin Study Samples  
[name]  
[name]  
[contact] or [contact]  
[contact]

## 5.2 Visit Schedule and Study Evaluation

### Screening

Total 30 patients (up to 40 consented), approximately 15 with HCC and 15 with secondary liver cancer (range: 8-20): Obtain informed consent, screen potential subjects by inclusion and exclusion criteria, register eligible participants, obtain MRI imaging and labwork if not already completed.

Assignment into lobar or  
superselective arm based on  
imaging and history

Lobar arm:  
15 subjects (8-20)

Superselective arm:  
15 subjects (8-20)

### Day 0

PK baseline blood draw performed prior to cTACE.

cTACE procedure, lobar vs superselective approach as assigned.

PK blood draws at: 5, 10, 20, 40 min, 1, 2, 4 hours after cTACE.

### Day 1

PK blood draw 24 hours after cTACE.  
Standard of care non-contrast abdomen CT to ensure Lipiodol administration.

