**# of Patients (planned):**

30 patients to be enrolled, approximately 15 patients with primary liver cancer and 15 patients with secondary liver cancer. Up to 40 patients may be consented if necessary in order to account for potential patients who screen-out or who are unable to complete sample collection for the PK (80% of planned draws). 15 patients will be assigned to the lobar treatment arm and 15 patients will be assigned to the superselective treatment arm.

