## 1. Introduction

### 1.1 Background/Rationale

Transarterial chemoembolization (TACE) is the combination of locally injected chemotherapy and embolization of the tumor feeding arteries. Due to good tumor response rates and a low incidence of side effects, this technique has evolved into the standard palliative treatment for a number of primary and secondary liver cancers, including hepatocellular, intrahepatic cholangiocellular, colorectal, and neuroendocrine cancer. Conventional TACE (cTACE), the first type of TACE developed, consists of the injection of a mixture of chemotherapeutic drugs with Lipiodol, an oil-based contrast agent, followed by the injection of small beads to occlude the tumor feeding arteries. Despite the local injection of the chemotherapeutic drugs, this technique was shown to result in a high serum concentration peak of the chemotherapeutic drugs right after injection. Drug-eluting beads were developed to release the chemotherapeutic agent over a longer period of time, resulting in a lower initial serum concentration and a higher concentration of the chemotherapeutic drug in the tumor treated area over time.

Since the development of drug-eluting beads, many research teams have focused on the advantages of Drug Eluting Bead TACE (DEB-TACE) over cTACE, including better tumor response and lower incidence of side-effects (1,2). Several PK studies comparing various bead types have been performed in different animal models (3-5). According to these studies, the serum concentration of chemotherapeutic drugs is lower using DEB-TACE compared to cTACE. However, the cTACE studies used for comparison date back to the 1990, at which time a variety of cTACE protocols were being used as the cTACE technique was still in its infancy. Over the years, several studies were performed to develop the optimal drug combination and delivery schema with regard to efficacy and toxicity (6, 7). To our knowledge, there is only a single, rather recent PK study comparing DEB-TACE to cTACE (8), however this study had only 5 patients in the c-TACE arm.

Thus, the purpose of this study is to perform a dedicated PK analysis of doxorubicin and its metabolite doxorubicinol after cTACE, and compare the PK profile of the two most widely used methods for cTACE, lobar and superselective.

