## 5. Study Design/Investigational Plan

### 5.1 Overall Design

The study is a single site, prospective study, designed to measure the PK of doxorubicin and its metabolite doxorubicinol at various timed intervals after cTACE in patients with primary or metastatic liver cancer.

Up to 30 patients will be enrolled that meet study entry criteria; approximately 15 with primary liver cancer and 15 with secondary liver cancer. Up to 40 patients may be consented if necessary in order to enroll these 30 patients, to account for potential patients who screen-out or who are unable to complete sample collection for the PK (80% of planned draws). 15 patients will be enrolled into the lobar cTACE arm and 15 patients will be enrolled into the superselective cTACE arm. The assignment of the treatment arm will be determined by the PI or a designated radiologist after review of the patient's imaging and history.

The study is planned to complete enrollment in two years, with another month to conclude patient follow-up.

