### 7.3 Statistical Plan

Up to 40 patients may be consented in order to enroll 30 patients, and to account for patients who are unable to complete sample collection for the PK (80% of planned draws). 15 patients will be enrolled into the lobar cTACE arm and 15 patients will be enrolled into the superselective cTACE arm.

We have assumed a clinically significant change in doxorubicin exposure would be 50%. In order to have 80% power to detect a 50% change with a 5%  $\alpha$ , the sample size varies depending on the variability noted with TACE therapy. In the Varella trial utilizing cTACE with a Lipiodol doxorubicin formulation, the variability was reported as 30% Coefficient of Variation (CV). In our recent trial (J1306) utilizing TACE with a Drug Eluting Bead (DEB) doxorubicin formulation, the variability was reported as 90% CV. We anticipate the Lipiodol formulation to behave more like the Varella trial with 15 patients allowing for slightly higher variability.

*%CV	30%	43%	90%
Expected Sample Size	8	15	58

\*Methodology/calculator accessed from the websites below on 11/6/2014:

[https://www.statstodo.com/SSizBioequiv\\_Tab.php](https://www.statstodo.com/SSizBioequiv_Tab.php)

[https://www.statstodo.com/SSizBioequiv\\_Pgm.php#](https://www.statstodo.com/SSizBioequiv_Pgm.php#)

Continuous variables will be reported as means and standard deviations, medians and ranges, or both. Categorical variables will be reported as numbers and percentages. Pharmacokinetic parameters will be calculated by standard noncompartmental methods using Phoenix WinNonlin 6.1 (Pharsight, Mountain View, CA) for each patient. Pharmacokinetic parameters will be summarized using descriptive statistics.

Comparisons of the pharmacokinetic profiles between the lobar cTACE group and the superselective cTACE group will be performed using the Mann-Whitney U test. Correlations between pharmacokinetic profiles and clinical toxicities will be performed using the Kruskal-Wallis one-way ANOVA test. Correlations between the pharmacokinetic profiles and tumor burden will be performed with the Spearman's correlation coefficient. A P value < 0.05 will be considered statistically significant in all cases.

HIC #: 1506016008  
[name]

Interim analysis:

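### Tumor type can be split unevenly between the lobar and superselective arms, and the planned unstratified comparison would read a tumor-type difference in exposure as a technique effect

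*Combined protocol and SAP*

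**What the plan says.** **Tumor-type quota.** Section 5.1 and the synopsis plan "approximately 15 with primary liver cancer and 15 with secondary liver cancer" in nearly the same words, with no range. The screening box of section 5.2 plans "15 with HCC and 15 with secondary liver cancer (range: 8-20", so it differs in the label and adds a range.

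**Arm quota.** Section 7.3 states that "15 patients will be enrolled into the lobar cTACE arm and 15 patients will be enrolled into the superselective cTACE arm". Section 5.1 and the synopsis agree. Section 5.2 gives 15 per arm with the range 8-20.

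**Total.** Section 5.2 has "Total 30 patients (up to 40 consented"; section 5.1 has "Up to 30 patients will be enrolled that meet study entry criteria".

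**Assignment.** Under section 5.1 the arm is chosen by the PI or a designated radiologist after looking at imaging and history. In the section 5.2 flow this comes after consent and registration.

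**Analysis.** Section 7.3 compares the arms by Mann-Whitney U test at P < 0.05, with no stratification or adjustment. Sections 2.1 and 7.1 list toxicity, tumor burden, BSA and gender as PK correlates; tumor type is absent. The interim analysis in section 7.3 reviews PK after 16 patients, about 8 per arm, and does not mention tumor type.

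**The concern.** The lobar-versus-superselective comparison is part of the primary outcome, and the synopsis says that the findings could change practice. The arms are formed by clinical choice, and the two sets of quotas are set independently. Nothing therefore keeps the mix of primary and secondary tumors similar in the two arms. If doxorubicin exposure differs by tumor type, the planned test attributes part of that difference to technique, in proportion to the imbalance.

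The plan balances tumor type overall but uses it in no analysis, so the imbalance would be neither reported nor corrected. If the arm-by-tumor-type cells were empty, no later adjustment could separate the two factors.

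**Working it through.** **1. The plan's own figure.** Section 7.3 tabulates 8, 15 and 58 patients for CVs of 30%, 43% and 90%, a 50% change, 80% power and 5% alpha. I read these as per arm, two-sided, with a 1.5-fold ratio on the log scale; the documents state none of these three. Then n = 2(1.96 + 0.84)² ln(1 + CV²) / (ln 1.5)².

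- CV 30%: 2 × 7.85 × 0.0862 / 0.1644 = 8.2, so 9
- CV 43%: 2 × 7.85 × 0.1697 / 0.1644 = 16.2, so 17
- CV 90%: 2 × 7.85 × 0.5933 / 0.1644 = 56.7, so 57

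Each is within two patients of the table. I use CV 43% below because it is the value behind the chosen 15 per arm.

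**2. What the quotas allow.** With 15/15 by arm and 15/15 by tumor type, let x be the number of primary tumors in the lobar arm. The four cells are x and 15 − x (lobar), 15 − x and x (superselective). Every x from 0 to 15 satisfies all quotas, including x = 0 and x = 15.

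**3. Bias in the arm ratio.** Suppose technique has no effect and AUC differs by a factor R between tumor types. R is an assumption, because the documents give no figure; I show 1.25 and 1.5. The apparent arm ratio is R raised to the difference in the share of primary tumors between arms.

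- 10:5 versus 5:10: difference 10/15 − 5/15 = 0.33; ratio 1.08 or 1.14
- 12:3 versus 3:12: difference 0.80 − 0.20 = 0.60; ratio 1.14 or 1.28
- 15:0 versus 0:15: difference 1; ratio 1.25 or 1.50

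**4. How often the planned test rejects.** Simulation with lognormal AUC, CV 43%, 15 per arm, two-sided Mann-Whitney at 5% and no technique effect. Repeated runs agree within about two percentage points.

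| Primary:secondary, one arm vs the other | R = 1.25 | R = 1.5 |
|---|---|---|
| 10:5 vs 5:10 | 6% | 9% |
| 12:3 vs 3:12 | 11% | 27% |
| 15:0 vs 0:15 | 28% | 70% |

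**5. The stratified test.** At 12:3 versus 3:12 a van Elteren test stratified by tumor type rejects in about 4-5% of trials, the nominal level. Its power for a true 1.5-fold technique difference is about 65% at 10:5 and 49% at 12:3, against about 71% for the unstratified test. With completely empty cells it cannot be computed.

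**6. The 8-20 range.** With exactly 30 patients and both groups capped at 20, 30 − 8 = 22 and 30 − 9 = 21 both break the cap, while 30 − 20 = 10. The attainable splits run from 10:20 to 20:10, eleven in all. Since 8 + 20 = 28, a group of 8 fits only if 28 or fewer enroll; a group of 9 needs 29 or fewer.

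**7. The label.** Section 1.1 lists TACE indications "including hepatocellular, intrahepatic cholangiocellular, colorectal, and neuroendocrine cancer", and section 3.2 admits any liver-dominant or liver-only malignancy. An intrahepatic cholangiocellular cancer is therefore eligible and counts as primary in section 5.1, but fits neither category in section 5.2.

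**The case against.** **The extreme case is not forecast.** This stands. A reader might infer from section 1.5 that superselective treatment goes with HCC and lobar treatment with metastases, so that strong confounding is likely. The section does not say so. It ties lobar treatment to several lesions within a lobe, and its remark on small HCCs reports necrosis in cited studies. Section 1.4 counts multinodular tumors among the best TACE candidates, in a discussion mostly about HCC, so HCC patients may well be treated in the lobar arm. No expected cross-split is given, and at 10:5 the inflation is small.

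**The tumor-type effect is assumed.** True, which is why it is shown as a range. The plan offers no evidence that the effect is nil.

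**The quota wording is harmless.** Largely right. A reader might infer that 8-20 is impossible with 30 patients. It is not: the planned 15/15 and ten other splits satisfy it, and only 8 and 9 are out of reach at exactly 30. The range can be read as a tolerance around the same target of 15; the floor of 8 matches the tabulated size at 30% CV and the interim count per arm. The HCC label excludes no patient and changes no planned result.

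**Uneven arms cost little power.** If the 50% change means a halving, simulated power is 99% at 15:15, 98% at 10:20 and 96% at 8:20. Arm size is not the problem.

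**A joint quota would be the direct cure.** It is hard to operate. Section 5.2 fixes the arm only after consent and registration, so a full cell could not be closed at consent. Patients would be turned away afterward, using up the allowance of 40 consents.

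**Tumor type is only one confounder.** This also stands. Lesion number and extent are what section 1.5 links to technique, and stratifying by tumor type does not remove them.

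**Conclusion.** The concern holds as a gap in the analysis plan. Arm is chosen clinically, tumor type and arm are balanced separately, and the only arm comparison ignores tumor type. The false-positive rate depends on two unknowns, the cross-split and the tumor-type effect: about 6-9% for a mild imbalance, 11-27% for a marked one and 28-70% for complete separation. These figures assume lognormal AUC, CV 43%, 15 per arm, and tumor-type ratios of 1.25 to 1.5 that do not come from the documents. Complete separation is permitted, not predicted.

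The label and the range in section 5.2 are real but minor inconsistencies. They do not make the enrollment plan infeasible.

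**What to change.** In section 7.3:

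- Add a van Elteren version of the arm comparison, stratified by primary versus secondary tumor.
- Report the PK parameters by tumor type within arm, with the arm-by-tumor-type counts.
- State that if a cell is empty or nearly so, the technique effect cannot be separated from tumor type, and that the arm comparison will be reported with that limitation.
- Review the arm-by-tumor-type table at the 16-patient interim look, in place of a hard joint quota.

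In section 5.2, write primary liver cancer, as in section 5.1 and the synopsis. Reconcile the 8-20 range with 30 patients (10-20 is the consistent range) and with the fixed 15 per arm in sections 5.1 and 7.3.

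**Cost.** Wording and one extra analysis on data already collected; no added patients or procedures. The stratified test loses power as the cells become unbalanced, as step 5 of the working shows. Confounding by lesion number and extent remains and should be acknowledged when the comparison is reported.
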